3.2.7 Other Exclusion Criteria

- 3.2.7.1 History or current clinical evidence of moderate-to-severe obstructive pulmonary disease or reactive airway diseases (i.e. asthma) requiring therapy.
- 3.2.7.2 Serum AST and/or ALT > 3 times upper limit of institutional normal.
- 3.2.7.3 Gastrointestinal, or biliary disorders that could impair absorption, metabolism, or excretion of orally administered medications.
- 3.2.7.4 Endocrine disorders (such as primary aldosteronism, pheochromocytoma, hyper- or hypothyroidism) not controlled with medication.
- 3.2.7.5 Uncontrolled diabetes (Controlled diabetes per the American Diabetes Association and International Diabetes Center's Glycemic Target Goals is Hemoglobin A1C < 7%).
- 3.2.7.6 Anemia (hematocrit < 28%).
- 3.2.7.7 Currently using select CYP2D6 inhibitor or inducer medications (full list, see [Section 6.1.7](#)).
- 3.2.7.8 Inability to swallow pills.

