7.1 Required Clinical, Laboratory and Disease Evaluations

Studies	PRIOR to Enrollment	Days on Study Drug										
	Eligibility Screening	1 st day of drug	14 ±2 calendar days	42 ±7 calendar days	90 [@]	180	270	365	455	540	630	730
History and physical	X		X	X	X [@]	X		X		X		X
Cardiac Evaluations												
Echocardiogram ^{&}	X					X		X		X		X
Electrocardiogram	X		X	X								
Lab Tests												
Pregnancy Test [*]	X											
Hematocrit Blood Draw	X											
Biomarkers Blood Draws (see Section 10.3)	X					X		X		X		X
CBC and Comprehensive Metabolic Panel (Creatinine, liver panel (bilirubin, AST/ALT))	X					X		X		X		X
Questionnaires (available in English and Spanish)												
Demographics, Medical and Family History Forms	X											
HRQoL Form	X					X		X		X		X
Treatment Management and Adherence Monitoring												
Follow-up phone call [#]					X [@]		X		X		X	
Symptom Log, Study Tablet dispersal		X	X	X	X	X	X	X	X	X	X	X [%]

& COG institutions will receive additional per-case reimbursement for this study to allow institutions to pay for the two echocardiograms (month 6 and month 18) that are not considered standard of care.

[@] For the Day 90 visit only, the patient has the option to do an in-person visit or a phone follow up, depending on their ability to easily return to the clinic. If Day 90 is a phone follow up, the History and Physical is not required.

^{*} Women of childbearing potential require a negative pregnancy test prior to starting study drug; females of reproductive potential may not participate unless they have agreed to use an effective contraceptive method during the study and for at least 2 months after the last dose of study drug. Abstinence is an acceptable method of birth control. For female participants of childbearing age, investigators will follow-up regarding their pregnancy status at each clinic visit. A pregnancy test is required at the eligibility screening and then throughout the study period as deemed necessary by the investigator.

[#] Follow-up phone calls are to confirm medication tolerance after the screening day and in-between clinic visits to determine (and reinforce) adherence, complete the Symptom Log, and arrange medication refill. The medication refills are either picked up by the patient or sent via FedEx to their home.

[%] No study medication is dispensed at Day 730.

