9.3.3 Objective Safety Measures

Adverse events. The number of Grade 2-4 toxicities observed will be tabulated by treatment arm. Differences by treatment arm will be evaluated using Fisher exact tests.

Biomarkers. Liver function measurements (Bilirubin, AST, ALT) will be treated as continuous variables. Study participants will be considered to have elevated liver function if the measurements at 6, 12, 18, and 24 months are above the upper limit of the institutional reference range and higher than baseline pre-treatment level. These data will be coded such that those who are greater than 2-times the upper limit of the reference range will be considered to be clinically significant (Grade 1 if asymptomatic and requiring no intervention; Grade 2 if minimal/local/non-invasive intervention required). The frequency of individuals with elevated liver function measures will be compared between treatment groups using an exact test on 2x2 tables, stratified on CYP2D6. Logistic regression analysis will also be used to compare the frequency of elevated liver function between treatments, adjusted for covariates. Linear mixed-effects model for normally distributed data will also be used to compare the trends in liver function levels between the treatment groups. Procs MIXED and GLIMMIX will be used for longitudinal analysis of normally and non-normally distributed data, respectively. Proc GENMOD will also be used for normally and non-normally distributed data.

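### The liver case rule sets no minimum rise over baseline although patients may enter with AST/ALT up to 3 times the upper limit, so stable patients with a raised baseline can become cases by chance

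*Combined protocol and SAP*

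**What the plan says.** Section 9.3.3 (Objective Safety Measures) defines a liver case in one sentence. Its opening names the visits: "Study participants will be considered to have elevated liver function if the measurements at 6, 12, 18, and 24 months". It then sets two conditions that must hold together, namely that these values "are above the upper limit of the institutional reference range and higher than baseline pre-treatment level". No size of rise is given, and the text does not settle whether one visit or all four must qualify, or how bilirubin, AST and ALT combine.

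A second tier follows: values "greater than 2-times the upper limit of the reference range will be considered to be clinically significant". It is labelled Grade 1 or Grade 2 according to symptoms and intervention, and it is not tied to a worsening from baseline.

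Section 3.2.7 gives the only liver entry limit, an exclusion for "Serum AST and/or ALT > 3 times upper limit of institutional normal". None of the listed criteria limits bilirubin. The schedule in Section 7.1 has one liver panel before treatment (screening), then panels at Days 180, 365, 540 and 730.

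On analysis, Section 9.3.3 says: "The frequency of individuals with elevated liver function measures will be compared between treatment groups using an exact test on 2x2 tables, stratified on CYP2D6". A covariate-adjusted logistic regression of the same cases is added. The levels themselves are also analysed: "Liver function measurements (Bilirubin, AST, ALT) will be treated as continuous variables", and a linear mixed-effects model "will also be used to compare the trends in liver function levels between the treatment groups".

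**The concern.** The baseline clause looks meant to separate new elevation from elevation already present at entry. For a patient who enters above the limit and stays there, the first half of the rule is always met. The rule then reduces to exceeding a single screening value by any amount, which ordinary variation can do.

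The higher tier does not repair this. A patient who enters at 2.8 times the limit and later reads 2.9 times is a case on that value and falls in the clinically significant tier, although almost nothing has changed.

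Aim 1.2.1 names hepatic function as its objective safety measure, and both frequency analyses use this definition. Cases that arise by chance in both arms make a real difference harder to see. In a safety comparison, a missed signal is the costlier error.

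**Working it through.** The documents give no expected rate, power or sample size for liver cases, so there is no liver figure to reproduce. As a check on method, the neighbouring adverse-event figures in Section 9.4 do reproduce with an exact two-sided Fisher test at 0.05: 56 per arm, 5% v 24.7%, gives power 0.800; 88 per arm, 5% v 19.2%, gives 0.802.

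**Inputs from the documents:** the case rule and four follow-up visits (9.3.3); AST/ALT entry limit of 3 times the upper limit (3.2.7); one baseline panel (7.1); 91 per arm and 19% attrition per year (9.4).

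**Assumed, because the documents give no figure:** within-person variation, the spread of levels between patients, the share with a raised baseline, and the true case rates.

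**Step 1: stable patient, true level clearly above the limit, one analyte.** Baseline and k follow-up values are exchangeable.

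- P(at least one follow-up exceeds baseline) = k/(k+1). For k = 4 this is 4/5 = 80%. For k = 1, 2, 3 it is 50%, 67%, 75%.
- P(all follow-ups exceed baseline) = 1/(k+1). For k = 4 this is 1/5 = 20%.
- With 19% attrition per year, about 90% are retained per half-year (√0.81 = 0.9). The shares with 0, 1, 2, 3 and 4 visits are 10%, 9%, 8.1%, 7.3% and 65.6%. The any-visit average is 0.09×0.50 + 0.081×0.667 + 0.073×0.75 + 0.656×0.80 ≈ 68% of those randomised.

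**Step 2: patient identified by one observed baseline between 1 and 3 times the limit.** Some such readings are high by chance and fall back. Lognormal simulation with median 0.5–0.7 times the limit, log-SD 0.3–0.5 and within-person CV 10–30%:

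| Reading | Lowest | Highest |
|---|---|---|
| Any visit | 34% | 74% |
| All four visits | 0.6% | about 15% |

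In the same runs, patients whose true level was above the limit gave 79–81% (any visit), in agreement with Step 1.

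**Step 3: cost in power.** Let f be the share with a raised baseline and c their chance case rate, equal in both arms. Each arm's case rate is f·c + (1−f)·p, with p = 3% v 15% (assumed). For f = 10% and c = 0.80 this gives 0.080 + 0.027 = 10.7% v 0.080 + 0.135 = 21.5%. Two-sided Fisher power, 91 per arm, unstratified:

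| c | f = 0 | 5% | 10% | 20% |
|---|---|---|---|---|
| 0.80 (any visit, upper) | 78% | 57% | 44% | 28% |
| 0.34 (any visit, lower) | 78% | 66% | 55% | 39% |
| 0.20 (all four, true level raised) | 78% | 69% | 61% | 45% |

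This formula lets raised-baseline patients contribute no treatment difference, so not all of the loss is noise. If chance cases are instead added on top of real ones, the rate is p + (1−p)·c·f. Power is then 58%, 45% and 30% at c = 0.80, and 68%, 60% and 49% at c = 0.34.

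The additive form applied to the plan's adverse-event rates (56 per arm, 5% v 24.7%, c = 0.80) takes power from 80% to 67%, 57% and 42% for f = 5%, 10% and 20%.

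**The case against.** Four points can be made for the plan.

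- **The visit rule.** A reader might infer that about 80% of stable patients with a raised baseline will become cases. The documents do not support that. The sentence lists four visits joined by 'and'; read literally, all four must qualify, and the figure is 20% at most for one analyte. Even with any visit counting, 80% needs a true level above the limit and full attendance. One raised screening value gives less because of regression to the mean. This stands, and the figures here are conditional for that reason. Settling the visit rule would not remove the defect, however: under either reading there is still no minimum rise.
- **No bias between arms.** A reader might also infer a spurious hepatic signal. Allocation is 1:1 and double-blind, so the noise falls on both arms alike. It costs power and creates no false difference. This stands in full.
- **Other analyses.** The mixed model uses the levels and does not depend on the cut-off, and Grade 2–4 toxicities are compared separately. So it cannot be said that Aim 1.2.1 rests on the case count alone. This stands in part: a model of mean trends can miss a few patients with large rises, which is what a case count is for, and covariate adjustment does not correct a misclassified outcome.
- **Assumed inputs.** Neither the share with a raised baseline nor 3% v 15% is in the documents. If few patients enter above the limit, the loss is small. This stands; the power figures are an illustration over a range.

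**Conclusion.** The point holds in a limited form. The rule counts any rise above one screening value, and eligibility admits patients for whom that is the only effective condition. The chance of becoming a case without real change is 80% (any visit) or 20% (all four) for a stable patient truly above the limit with all visits and one analyte. It is about 34–74% or 1–15% for patients identified by one raised reading, under the assumed distributions. Counting any of three analytes would raise these figures; missed visits lower the any-visit figure.

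The consequence is dilution of the exact test and the logistic regression of liver cases. In the illustration, power falls from 78% to 57–66%, 44–55% and 28–39% for 5%, 10% and 20% with a raised baseline on the any-visit reading, and by less on the all-visits reading. The number of chance cases in this trial cannot be derived from the documents. The continuous analysis is untouched. Priority is low to moderate: a cheap improvement to a secondary safety analysis.

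**What to change.** Change the analysis case definition in Section 9.3.3 only; eligibility and patient care are not involved.

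- Count a case only when the value is above the institutional upper limit and its CTCAE v5.0 grade (the scale adopted in Section 12.1) is worse than the grade of that patient's own baseline value.
- Apply the same condition to the tier above 2 times the limit.
- Use this one scale throughout the paragraph in place of the separate Grade 1/2 coding by symptoms and intervention.
- Apply the rule to bilirubin, AST and ALT alike, and say how the three combine.
- State whether any one visit or all four must qualify.

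The protocol cites the CTCAE grade limits but does not reproduce them, so the remaining noise rate cannot be computed from the documents, and a patient close to a grade limit could still cross it by chance. As a guide to what a minimum rise achieves (stable patient well above the limit, any of four visits), the 80% drops to 0.8%, 20% and 38% at within-person CV 10%, 20% and 30% if a rise above 1.5 times baseline were needed, and to 0%, 2% and 14% if above 2 times. These multiples are illustrations, not proposals.

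The cost is a short change of wording, with no new data or visits. Small within-grade rises in raised-baseline patients stop counting as cases, but the planned mixed model still uses them. Patients with a normal baseline are classified as before, provided any value above the limit grades worse than a normal one.

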1.2 Secondary Aims

1.2.1 To establish safety and tolerability of this two-year course of low-dose carvedilol, assessing both objective measures (hepatic function) and patient reported outcomes.

1.2.2 To examine the modifying effect of demographic, clinical, and molecular characteristics on the risk: benefit ratio from this two-year carvedilol intervention.

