9.5 Interim Monitoring

9.5.1 Toxicity Criteria for Study Stopping

If, on either arm, two or more cases of the same Grade 3-4 toxicity with *probably* or *definitely* attributions that do not resolve in 72 hours are reported in separate patients, accrual will be held until further review by the DSMC to determine whether or not the study should be stopped based on the unblinded data available at that time.

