12.0 EVALUATION CRITERIA**12.1 Common Terminology Criteria for Adverse Events (CTCAE)**

This study will utilize version 5.0 of the CTCAE of the National Cancer Institute (NCI) for toxicity and performance reporting. A copy of the CTCAE version 5.0 can be downloaded from the CTEP website

http://ctep.cancer.gov/protocolDevelopment/electronic_applications/ctc.htm.

Additionally, toxicities are to be reported on the appropriate case report forms.

Please note: 'CTCAE v5.0' is understood to represent the most current version of CTCAE v5.0 as referenced on the CTEP website (i.e., v5.02 and all subsequent iterations prior to version 6.0).

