13.3 Reporting of Adverse Events for Commercial Agents - via CTEP-AERS

Expedited AE reporting must use CTEP-AERS (Adverse Event Expedited Reporting System), accessed via <https://eapps-ctep.nci.nih.gov/ctepaers>

Commercial reporting requirements are provided in Table B. The commercial agent(s) used in this study are listed in the front of this protocol immediately following the Study Committee roster.

- COG requires the CTEP-AERS report to be submitted **within 7 calendar days** of learning of the event.
- Use the NCI protocol number and the protocol-specific patient ID provided during trial registration on all reports.

CTCAE term (AE description) and grade: The descriptions and grading scales found in the revised NCI Common Terminology Criteria for Adverse Events (CTCAE) version 5.0 will be utilized for AE reporting. All appropriate treatment areas should have access to a copy of the CTCAE version 5.0. A copy of the CTCAE version 5.0 can be downloaded from the CTEP website at:

http://ctep.cancer.gov/protocolDevelopment/electronic_applications/ctc.htm.

Table B

Reporting requirements for adverse events experienced by patients on study who have NOT received any doses of an investigational agent on this study.

CTEP-AERS Reporting Requirements for Adverse Events That Occur During Therapy with a Commercial Agent or Within 30 Days¹

Attribution	Grade 4		Grade 5
	Unexpected	Expected	
Unrelated or Unlikely			CTEP-AERS
Possible, Probable, Definite	CTEP-AERS		CTEP-AERS

¹This includes all deaths within 30 days of the last dose of treatment with a commercial agent, regardless of attribution. Any death that occurs more than 30 days after the last dose of treatment with a commercial agent that can be attributed (possibly, probably, or definitely) to the agent and is not due to cancer recurrence must be reported via CTEP-AERS.

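### Section 9.3.3 grades liver values above twice the upper limit by symptoms and intervention only, stops at Grade 2, and is not reconciled with the CTCAE v5.0 grading adopted in Sections 12.1 and 13.3

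*Combined protocol and SAP*

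**What the plan says.** Aim 1.2.1 sets out to establish safety and tolerability, "assessing both objective measures (hepatic function) and patient reported outcomes". Hepatic function is the only objective measure it names.

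Section 9.3.3 has two paragraphs. The first, on adverse events, tabulates Grade 2-4 toxicities by arm and compares them with Fisher's exact test. The second, on biomarkers, deals with bilirubin, AST and ALT. A participant counts as elevated when the follow-up measurements are "above the upper limit of the institutional reference range and higher than baseline pre-treatment level". A second coding follows: "those who are greater than 2-times the upper limit of the reference range will be considered to be clinically significant", with the grades "Grade 1 if asymptomatic and requiring no intervention; Grade 2 if minimal/local/non-invasive intervention required".

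The same paragraph treats the liver values as continuous and compares their trends between arms with mixed models. It compares the frequency of elevated participants by an exact test stratified on CYP2D6 and by logistic regression.

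On grading in general, Section 12.1 states: "This study will utilize version 5.0 of the CTCAE of the National Cancer Institute (NCI) for toxicity and performance reporting". Section 13.3 says of the CTCAE that "version 5.0 will be utilized for AE reporting". Grade then drives several rules: the accrual hold in 9.5.1 ("two or more cases of the same Grade 3-4 toxicity"), and in 13.4 routine reporting from Grade 2 and the unblinding and off-therapy rule from Grade 3, all limited to probable or definite attribution.

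**The concern.** The liver rule in 9.3.3 uses the word Grade in the same section as the Grade 2-4 table, but it is not the scale that 12.1 and 13.3 adopt. It ignores how large the rise is and cannot produce a Grade 3 or 4. A site and an analyst could therefore grade one laboratory result under different rules, with nothing in the plan to settle which grade is used.

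What is at stake is how the named hepatic safety measure is reported. A laboratory abnormality can be large without symptoms. If the categorical summaries cannot separate a marginal rise from a marked one, an imbalance between arms in marked rises could go unreported even though the data are in hand.

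**Working it through.** **Inputs.** The liver coding, the elevated definition and the liver analyses come from 9.3.3, the adopted scale from 12.1 and 13.3, and the grade-driven rules from 9.5.1 and 13.4. The entry limit is in 3.2.7.2: "Serum AST and/or ALT > 3 times upper limit of institutional normal". The adverse event power statement is in 9.4 (Amendment #4). The CTCAE v5.0 liver criteria are not reproduced in the documents, so nothing below uses them.

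**Step 1. The plan's own figure.** The nearest stated number is the power for the Grade 2-4 comparison: 5% against 24.7%, 56 per arm, Fisher's exact test, alpha 0.05, at least 80%. The remaining sample is 91 × (1 − 2 × 0.19) = 91 × 0.62 = 56.4, hence 56. Exact enumeration of two independent binomials with a two-sided Fisher test gives 0.8002. The figure reproduces, and this point disputes no number in the plan.

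**Step 2. Apply 9.3.3 to three ALT values.** Each is asymptomatic, needs no intervention and is above the patient's baseline.

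| ALT, multiple of upper limit | Elevated | Above 2 times | Grade under 9.3.3 |
|---|---|---|---|
| 1.1 | yes | no | none |
| 2.1 | yes | yes | 1 |
| 10 | yes | yes | 1 |

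A value of 10 is 10/3 = 3.3 times the entry limit, yet it gets the same grade as 2.1. The entry limit is not a grading cut-point. It shows only that the protocol treats size as informative elsewhere.

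**Step 3. What the rule leaves out.** A value above twice the limit has no grade if the patient has symptoms but needs no intervention, or if more than minimal intervention is needed. Grades 3 and 4 cannot occur at all, although 9.5.1 and 13.4 act on them.

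**Step 4. Which liver analyses use size.**
- The mixed models use the actual values, so size enters. They compare average trends, in which a few extreme values can be diluted.
- The exact test and the logistic regression use elevated yes/no. All three rows of the table count equally.
- The class above twice the limit has no stated comparison between arms.

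No stated categorical analysis therefore compares marked elevations between carvedilol and placebo.

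**Step 5. Can the loss be sized?** Not from the documents. Purely as an illustration, suppose a share of Grade 2-4 events in both arms were recoded as Grade 1. The power of 0.80 would fall to 0.74 for a share of 10%, 0.61 for 25% and 0.35 for 50%. The documents give no such share, and they do not say that this recoding happens.

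**The case against.** The strongest reply is that the parenthetical grades are only a label for a laboratory variable. They stand in the biomarker paragraph, whereas the toxicity table is in the adverse event paragraph. Sections 12.1 and 13.3 assign reporting to CTCAE v5.0, and no passage sends the 9.3.3 code into the Grade 2-4 table, routine reporting or the accrual hold. Size is also not lost altogether, because the values are analysed as continuous and the elevated threshold is lower than twice the limit.

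Most of this stands, and it rules out three stronger readings that a reader might infer.

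- *The 9.3.3 grades contradict the CTCAE liver cut-points.* This cannot be checked, because the documents do not contain those criteria.
- *Large asymptomatic rises escape the toxicity table and the Grade 3-4 rules.* This would need the 9.3.3 code to feed them, and the text does not say that it does.
- *An asymptomatic rise of any size is Grade 1, so no laboratory-only event can reach Grade 2.* The rule starts only above twice the limit, and Grade 1 also requires that no intervention is needed. An asymptomatic rise that needs minimal intervention is Grade 2.

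The reply does not remove the narrower point. The plan never says that the grades are a label only. Even on that reading, two sets of liver grades exist under one word, and marked elevations still have no comparison by arm.

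**Conclusion.** The point holds as an unreconciled grading rule combined with a gap in the liver analysis. The plan has two possible gradings for one liver value and does not say which one counts. The 9.3.3 version is blind to size above twice the limit and ends at Grade 2. The categorical comparison pools everything above the upper limit and above baseline.

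Its size is qualitative: 2.1 and 10 times the limit share a grade, and 1.1 and 10 times share a category. No bias or loss of power can be put on it. The conclusion assumes that the frequency comparison in 9.3.3 uses the elevated definition given just before it, which is how the sentence reads. It does not depend on the content of CTCAE v5.0, or on the 9.3.3 code reaching the adverse event table. The primary endpoint is unaffected. The correction should be made because it concerns the one objective safety measure named in the aims and is cheap.

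**What to change.** In 9.3.3, delete the parenthetical grades. Grade bilirubin, AST and ALT by the CTCAE v5.0 scale already adopted in 12.1, with these conditions:

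1. Count only post-baseline values higher than the patient's own baseline, as 9.3.3 already requires for elevated. Patients may enter with AST or ALT up to 3 times the limit, so without this condition an unchanged entry abnormality would be counted as a new finding.
2. Report each patient's worst grade by arm in a separate laboratory table, regardless of attribution. Routine reports are limited to probable or definite attribution, so merging the two would change the endpoint behind the assumed 5% placebo rate.
3. Keep the flag for values above twice the limit as a descriptive category.
4. State that the Grade 2-4 toxicity table and the Grade 3-4 rules use CTCAE grades only. This settles which scale applies and leaves the thresholds and actions in those rules as written.

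The cost is wording and programming. Sites already record the liver values on the Site Lab Values Form, and 9.3.3 already relies on institutional limits, so no visits or samples are added. The stated liver safety profile may look slightly less favourable.
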